Background and Significance: Only 15-30% of patients who suffer in-hospital cardiac arrest (IHCA) survive to hospital discharge.^{1,2} Factors associated with lower mortality and improved function include provision of high-quality, minimally-interrupted chest compressions, prompt administration of epinephrine, and swift defibrillation of eligible arrhythmias.³⁻⁶ Unfortunately, resuscitation teams provide suboptimal care to 25-40% of IHCA victims, with significant variation in IHCA outcomes and process adherence documented between hospitals.^{3,7} Resource limitations and less-experienced providers may explain lower IHCA at small hospitals and on nights and weekends.^{8,9} Although educational and technological interventions may improve patient outcomes, the gap between optimal and actual resuscitation practice remains large.^{1,10} Barriers to effective IHCA resuscitation countered by effective leadership include response teams’ ad hoc formation and variable structure and member expertise.¹¹⁻¹³ Explicit leadership training improves processes of care and outcomes for IHCA resuscitation, but standard Advanced Cardiac Life Support (ACLS) training provides little instruction non-technical skills critical for high-functioning IHCA teams.^{12,14,15} A dedicated, leadership-trained “copilot” on cardiac arrest resuscitation teams may improve IHCA outcomes by performing the same functions — parallel analysis, situational awareness augmentation, action checking, protocol verification, and error correction — for the resuscitation team leader that an airplane copilot provides the pilot during an in-flight emergency. Employing telemedical technology to involve the “copilot” physician will allow this role to be filled by an intensivist physician with particular expertise in care of critical illness and will provide long-term cost and resource efficiencies, particularly in smaller hospitals with fewer available physicians.

Research subjects: We will conduct mock codes at Intermountain Healthcare hospitals, specifically Intermountain Medical Center, LDS Hospital, Riverton Hospital, The Orthopedic Specialty Hospital, McKay-Dee Hospital, Park City Medical Center, and American Fork Hospital.

- Local IHCA team: Intermountain Healthcare employees, resident physicians, and affiliated care providers who are either designated members of each participating hospital’s IHCA response

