teams or act as voluntary responders to announced mock codes will be eligible to participate. The number of on-site participants for each simulated IHCA event is expected to average 15-25.

- Telemedical intensivist IHCA copilot: Board-certified or board-eligible critical care medicine physicians on the staff of the Intermountain Healthcare Telecritical Care Center will act as IHCA team copilot. The total number of expected participants is up to 30.

Recruitment:

- Local IHCA team: IHCA team activation will employ the participating hospital's standard mechanism. A sign posted outside the room used for the mock code will indicate that a video-recorded simulation is taking place. After completion of the simulation, participants will receive an information sheet about the study.
- Telemedical intensivist IHCA copilot: Eligible telemedical intensivists will be invited to participate by email and in person.

Methods/Procedures:

- Study design: Randomized, multicenter, simulation-based clinical trial
- Intervention: Standardized consultation to IHCA team by off-site intensivist via two-way audiovisual link using a mobile telemedicine cart
- Control: Display of silent, pre-recorded, non-interactive videotape of an ICU physician. The on-site participants will be told that an intensive care physician is observing the mock code.
- Randomization: Each event will be randomly assigned to intervention or control using block randomization by hospital.
- Procedures:
 - All event will be randomly pre-assigned to intervention (participation via telemedicine link by a remote critical care physician) or control (prerecorded video of telemedicine physician displayed on mobile telemedicine cart).
 - A research coordinator will arrange a time for mock code with local hospital clinical leadership and Code Blue leadership. The remainder of the IHCA team will not be informed that the announced event is a simulation prior to team activation.
 - The research coordinator and an experienced simulation technician will set up simulation equipment in an unused patient care room on the general medical or surgical ward at the hospital, including video recording device and mobile telemedicine cart.
 - Research coordinator will obtain final confirmation with the on duty clinical leadership that simulation will not interfere with patient care.
 - The hospital's on duty IHCA resuscitation team will then be activated via the hospital's standard mechanism.

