 - Upon arrival to the room, members of the designated IHCA team and other care providers will be informed via a posted sign that the event is a videorecorded research simulation. They will then begin participate in the simulation at their discretion.
 - We will adapt existing, tested cardiac arrest simulation scenarios for use in this study. While the provided case histories will describe patients of different ages, genders, and presenting complaints, all scenarios will feature cardiac rhythms demanding substantively identical resuscitative actions (Figure 1).
 - The telemedical link (or a control video) will be activated by the research coordinator after the arrival of the team lead or after five minutes have elapsed, whichever occurs first. At this time, the coordinator will also provide simple, brief, and scripted "just-in-

time” training to the mobile telemedicine cart and, for intervention events, the telemedical intensivist copilot.

- For mock codes randomized to intervention, critical care physicians with experience in telecritical care who consent to participate in this study will provide standardized consultation to the on-site team. These IHCA team “copilots” will advice and assistance to the on-site team leader including help with ensuring high-quality, minimally-interrupted chest compressions and prompt defibrillation, assisting situational awareness, encouraging etiologic evaluation, and promoting leadership behaviors.
- The event will be terminated when team performs an action that was pre-determined for the scenario to result in return of spontaneous circulation. The simulation will be terminated no later than 25 minutes after initiation if team fails to perform this pre-determined action. Most simulations are expected to last 10-12 minutes.
- After simulation termination, participants will complete a brief, anonymous questionnaire.
- Local code team leadership and/or the on-site code team leader will lead a debrief of the event. As needed, the research coordinator or simulation specialist will facilitate discussion of the simulation.
- In progress mock code simulations may be terminated by on-duty hospital clinical leadership or physician code team members if clinical care of patients requires.

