- Mock codes terminated in progress due to competing clinical priorities prior to simulated return of spontaneous circulation will be excluded from the final analysis. If this occurs, the simulation event may be rescheduled at the same hospital for a later date, with the rescheduled mock code assigned to the same study arm as the aborted mock code.
- If systematic problems interfering with study implementation, data collection, or interpretation are identified after study initiation, the study may be halted temporarily while the systematic issues are addressed. Affected events where data is invalid will be considered part of a roll-in phase of the study and will be excluded from data analysis. For each assigned to roll-in event status, we will schedule a make-up event at the affected hospital. Make-up events will be assigned to the same study arm as the roll-in event being replaced and will be interposed randomly with other events at the affected study site.
- Data collection: A research coordinator will be present at all mock codes. Besides study implementation duties, the coordinator will record team composition and function, processes of care, and leadership behaviors. Additional data will be obtained from (1) the simulator device, (2) the defibrillator device, (3) videotaped recording obtained via the mobile telemedicine carts, and (4) a brief questionnaire completed by IHCA team members upon completion of the mock code.
- The primary outcome for the study will be the fraction of time between activation of the telemedicine cart and beginning of the pulse check following the subsequent second full cycle of CPR that the IHCA team does not deliver chest compressions (“no-flow fraction”). Secondary outcomes are shown in Table 1.
 - On-site IHCA team members will complete a brief questionnaire (attached) to measure the subjective experience of individual and team function and — when applicable,

[figure not shown]

Figure 1. Unified structure for mock code scenarios. (ROSC: return of spontaneous circulation.)

opinions about the simulated mock code. Some on-site study participants will also complete a short-form version of the State-Trait Anxiety Index (STAI)¹⁶ validated for measurement of state anxiety (i.e. anxiety/stress at the time the questions are answered).¹⁷ Some participants may complete the survey online using REDCap, a secure web application for building and managing online surveys and databases.¹⁸

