- Off-site IHCA team copilots will complete a brief questionnaire (attached). Most participants may complete the survey online using a version of this questionnaire implemented in REDCap.¹⁸ Opinions about the procedure will also be elicited through post-study qualitative interviews.
- ACLS protocol adherence and violations using a checklist adapted from previously validated research tools.^{8,40}
- Leadership behaviors will be evaluated according to a previously published taxonomy.¹⁹
- Overall function of the IHCA team will also be evaluated using a previously validated instrument.^{20,21}
- Number of simulation events and power analysis: Assuming a baseline no-flow percentage of 0.285,^{10,22} a best-case no-flow fraction of 0.08 (protocol guidelines advise a single 10 second pause in chest compressions for a pulse and cardiac rhythm check every two minutes), and equipment malfunction or simulation termination precluding event analysis for 15% of mock codes, we will require 76 completed mock codes (38 in each arm) to achieve 80% power to detect a 31% relative decrease (9% absolute decrease) in the mean no-flow fraction.
- Study duration: The 76 planned mock codes will be divided between the 7-8 participating institutions. We expect to complete 2-6 simulations at each participating hospital every 2 months. Accounting for scheduling conflicts and expected intermissions during implementation of a new electronic medical record at some study hospitals, we expect study completion to require 18-24 months (and potentially up to 48 months) after simulations begin.

Informed consent (“copilot” physicians): Members of the research team will approach the eligible subjects by email (see attached) or in person at their workplace. Interested subjects will be consented by research team member(s) according to the Intermountain Healthcare Informed Consent Policy.

Table 1: Descriptive & outcome measures for randomized trial of telemedical intensivist IHCA team copilot

Variable	Data source	
	Primary	Secondary
Response team characteristics		
Response team structure	In-person observation	Video recording
Past experience of code team members	Questionnaire	
Primary outcome		
Fraction of pulseless time with no chest compressions*	Simulator mannequin	
Secondary outcomes		
Time from onset of shockable rhythm to defibrillation	Simulator mannequin	Defibrillator
Fraction of chest compressions in target depth range^{23*}	Simulator mannequin	Defibrillator

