Between-group comparisons for continuous variables will employ two-sided t-tests with unequal variance. Comparisons for binary or categorical variables will employ Fisher's exact test or chi-squared test as appropriate. Given clustering within simulations, between-group comparisons of survey responses will employ multilevel logistic (for binary variables) or linear (for continuous variables) regression with a random effect for simulation event. Comparisons of Likert-style variables will use the rank-sum method described Datta/Satten.²⁸

Sample size/power analysis: Assuming a baseline no-flow percentage of 0.285, a best-case no-flow fraction of 0.08 (protocol guidelines advise a single 10 second pause in chest compressions for a pulse and cardiac rhythm check every two minutes), and equipment malfunction or simulation termination precluding event analysis for 15% of mock codes, we will require 76 mock codes (38 in each arm) to achieve 80% power to detect a 31% relative decrease (9% absolute decrease) in the mean no-flow fraction. We therefore expect to enroll 1900 on-site IHCA team members as study subjects (although some participants may participate in >1 mock code).

Waiver of Informed Consent and HIPAA Authorization (for on-site IHCA team members):

We are requesting a waiver of informed consent and HIPAA authorization for on-site IHCA team study participants of this study. Participation in this study is similar to standard training for IHCA team members and involves no more than minimal risk to the subject. Individuals will be notified by means of a prominently displayed poster(s) that a simulation-based research project with video recording is in progress. Such notification will address individuals reasonable expectation of privacy. We will not use video recordings for any purposes except research, and digital video recordings will be stored securely and then transferred to a secure, approved server of the Intermountain network. We will not systematically collect individually identifiable information. The research therefore involves no more than minimal risk to the subjects; the only potential risk is a breach of confidentiality, and protections are in place to safeguard the data. Because risk is minimal, the waiver of consent and authorization will not adversely affect the rights or welfare of subjects.

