Data Collection: A research coordinator will be present at all mock codes. Besides study implementation duties, the coordinator will record team composition and function, processes of care, and leadership behaviors. Additional data will be obtained from (1) the simulator device, (2) the defibrillator device, (3) review of video recording of simulation event, (4) a brief questionnaire completed by IHCA team members upon completion of the mock code, and (5) a brief questionnaire completed by the telemedical physician copilot.

Data elements for collection

- Telemedical critical care physician (“copilot”)
 - Name
 - DOB
 - Email
 - Telephone
 - Race/ethnicity
 - Year completed medical school
 - Year completed post-graduate training
 - Date of first experience with telecritical care
 - Telecritical care shifts per year
 - Sex
 - Age
 - Credential type (MD vs DO)
 - Experience with in-person cardiac arrest events led
 - Date/time of each study simulation participation
 - Opinions about impact, utility, and feasibility of “copilot” interaction (survey)
 - Opinions about impact, utility, and feasibility of “copilot” interaction (post-participation qualitative interview)
- On-site code team participants
 - Event ID
 - Profession
 - Specialty (if physician)
 - Role on IHCA team
 - IHCA team participation frequency
 - Experience participating in mock code
 - Opinions about code team function during mock code
 - Opinions about impact, utility, and feasibility of “copilot” interaction
 - Short form State-Trait Anxiety Inventory^{16,17}
- Simulation events (see also Table 1)
 - Location
 - Date/time of event
 - Participant numbers and professions
 - Simulation duration
 - Date/time of key response parameters (i.e. team leader arrival)
 - Date/time of key resuscitation events
 - CPR quality
 - Interventions by IHCA team
 - ACLS protocol adherence
 - ACLS protocol deviation & errors

- Etiology identification
- IHCA team function
- Debriefing (Y/N) and themes
- Telemedicine interface function
- Leadership behaviors by IHCA team leader

Privacy, Confidentiality and Data Management

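### The trial randomises in blocks by hospital, but the primary Welch t-test ignores hospital; if hospital is prognostic, the test is conservative and gives up power.

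*Combined protocol and SAP*

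**What the plan says.** Under Methods/Procedures, Randomization: "Each event will be randomly assigned to intervention or control using block randomization by hospital". The block size is not given. Under Study duration: "The 76 planned mock codes will be divided between the 7-8 participating institutions". The title page lists nine sites and Research subjects names seven.

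Under Data analysis: "Between-group comparisons for continuous variables will employ two-sided t-tests with unequal variance". That sentence covers continuous variables in general. It governs the primary outcome because no other test is named for it. The plan contains no hospital term, stratified test or hospital-adjusted sensitivity analysis. Its only clustering term is a random effect per mock code, and that is for questionnaire responses only.

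On whether hospitals differ, Background and Significance describes resuscitation care "with significant variation in IHCA outcomes and process adherence documented between hospitals" and adds: "Resource limitations and less-experienced providers may explain lower IHCA at small hospitals". Against this, Procedures says that "all scenarios will feature cardiac rhythms demanding substantively identical resuscitative actions". Location is among the simulation-event items under Data elements for collection.

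**The concern.** Blocking by hospital makes the arms nearly equal in hospital mix, so hospital differences largely cancel from the arm comparison. An unadjusted t-test does not know this. It estimates its error from the total spread within each arm, hospital differences included. When hospital matters, the reported standard error exceeds the true one.

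What is at stake is efficiency: wider intervals, and a lower chance of detecting a real effect than the design supports. Each mock code needs a coordinator, a simulation technician, a telemedicine cart and clearance from clinical leadership, and the study may run up to 48 months, so information is expensive here.

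**Working it through.** **Inputs from the documents:** 76 mock codes, 38 per arm; 80% power; 0.09 absolute decrease from 0.285; 15% of events lost; 7-8 hospitals. **Assumed, because not stated:** two-sided alpha 0.05, SD, ICC (the share of total variance lying between hospitals) and block size.

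**1. The plan's own figure.** The 76 cannot be reproduced forwards without an SD, so the SD is solved backwards: SD = 0.09 / [(1.960 + 0.842) × √(2/n)].
- n = 38 per arm: 0.09 / (2.802 × 0.2294) = 0.140, or 0.138 with the noncentral t.
- n = 32 per arm, with the 15% loss inside the 76 (64/0.85 rounds up to 76): 0.09 / (2.802 × 0.25) = 0.128, or 0.126 with the noncentral t.

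Both cases are carried forward. One statement of the sample size calls the 76 mock codes completed and the other does not, so it is unclear whether the loss is inside the 76.

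**2. Mechanism.** Let σ² be the total variance, ρ the ICC, n = 38 per arm, and m the number of events per arm at a hospital, equal in the two arms.
- True variance of the arm difference: 2σ²(1 − ρ)/n.
- Expected Welch variance: (2σ²/n) × [(1 − ρ) + cρ], where c = (n − Σm²/n)/(n − 1).

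Take eight hospitals with 10, 10, 10, 10, 10, 10, 8 and 8 events. Then Σm² = 6×25 + 2×16 = 182 and c = (38 − 4.79)/37 = 0.898. The ratio of Welch to true standard error is √[(1 − 0.102ρ)/(1 − ρ)]:
- ρ = 0.10: 1.05
- ρ = 0.20: 1.11
- ρ = 0.30: 1.18

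Simulation gives 1.05, 1.10 and 1.17. With exact balance within hospital, the adjusted and unadjusted point estimates coincide, so only the standard error changes.

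**3. Power and type I error.** 20,000 simulated trials per setting, the hospital sizes above, normal outcomes and an effect of 0.09. Adjusted means hospital fixed effects with HC2 standard errors.
- A: 76 analysed, balanced within hospital, SD 0.138.
- B: blocks of 4, 15% random loss (about 65 analysed), SD 0.126.

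| ICC | A power, Welch / adjusted (%) | A Welch type I (%) | B power, Welch / adjusted (%) | B Welch type I (%) |
|---|---|---|---|---|
| 0 | 79.8 / 79.6 | 5.0 | 80.1 / 78.9 | 5.2 |
| 0.02 | 80.0 / 80.5 | 4.9 | 80.5 / 79.8 | 5.0 |
| 0.05 | 80.6 / 81.7 | 4.6 | 80.9 / 81.0 | 4.8 |
| 0.10 | 81.3 / 83.7 | 4.2 | 81.5 / 82.9 | 4.5 |
| 0.20 | 83.2 / 87.9 | 3.2 | 82.8 / 87.0 | 3.8 |
| 0.30 | 85.0 / 91.6 | 2.4 | 84.2 / 91.0 | 3.2 |

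Type I error of the adjusted test is 5.1% throughout A and B. B loses events without replacement. The protocol allows an aborted event to be rerun, with "the rescheduled mock code assigned to the same study arm as the aborted mock code", which partly preserves balance, so B is the less favourable case.

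**4. Sensitivity.**
- Unequal hospital sizes (20, 16, 12, 8, 8, 4, 4, 4) with blocks of 4 and 15% loss, Welch / adjusted power: 81.1 / 80.2 at ICC 0, 82.6 / 84.0 at 0.10, 83.9 / 87.9 at 0.20 and 85.5 / 91.7 at 0.30.
- Seven hospitals, or blocks of 2, give the same pattern.
- Arm SDs of 0.15 and 0.10, either way round, with about 34 and 30 analysed: adjusted minus Welch power is -0.7 to -1.5 points at ICC 0, +0.7 to +1.9 at 0.10 and +3.4 to +4.5 at 0.20. HC2 type I error is 5.4-5.6%, against up to 6.0% for model-based standard errors.

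**5. Interval width in setting A.** The mean 95% half-width falls from 0.0625 to 0.0597 at ICC 0.10, and from 0.0621 to 0.0563 at 0.20. The squared ratios are 1.10 and 1.22, worth roughly 7 and 16 extra events on a base of 76.

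**The case against.** The strongest reply is that nothing the plan promises fails. Welch is valid, its power in the table rises with ICC, and the 80% target is met. That is right, and it limits the point to efficiency.

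Second, the condition is not established for this outcome. The background evidence concerns real arrests, not simulated no-flow fraction. The sites belong to one system and the scenarios demand the same actions. The primary window is short, and teams form ad hoc, which puts variation between events within a hospital. All of this may lower the ICC. It stands as a reason to read the upper rows of the table with caution.

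Third, the simulations assume hospital differences of equal size in both arms. If the copilot halves them in the intervention arm, the gain falls to about +0.7 to +1.5 points at ICC 0.10, +1.7 to +2.6 at 0.20 and +3.3 to +3.9 at 0.30. If it removes them, the gain is under about 1.5 points up to ICC 0.30. The documents state no such interaction. Even with it, adjustment is level or better apart from the roughly 1-point cost.

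Fourth, normal outcomes with mean 0.195 and SD 0.138 put about 20% of intervention events below the protocol's best case of 0.08 and about 8% below zero. The powers are therefore a guide to size, and their decimals should not be relied on. Fifth, HC2 runs slightly above 5% when arm variances differ. That is a small but real cost.

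**Conclusion.** The point holds as a conditional one. Randomisation is blocked by hospital and the primary test omits hospital; if hospital is prognostic, the test is conservative and forgoes power. There is no bias and no inflation of type I error. The stated 80% power is not undercut provided the planning SD is the total SD.

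The difference is negligible if hospital explains about 5% or less of the variance. It becomes worth having from about 10%, and reaches 4 to 5 points at 20%. These sizes rest on the assumed alpha, SD, ICC range and block size, and on equal hospital effects in both arms. This is an inexpensive improvement to consider.

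**What to change.** Pre-specify the primary analysis as a linear regression of no-flow fraction on arm with hospital as a fixed effect, HC2 (or HC1) standard errors, and a t reference on the residual degrees of freedom. This keeps the allowance for unequal variances that motivated Welch. Avoid HC3 at this sample size: at ICC 0.10 its power is 80.3% against 83.7% for HC2 in setting A, and 78.8% against 82.9% in B. Keep the Welch test as a sensitivity analysis, and use the same regression for the other event-level continuous outcomes.

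The cost is SAP wording and one model term, with no new data. With 7 to 9 hospitals it uses 6 to 8 degrees of freedom out of about 65-76 events. If hospital explains nothing, it costs about 1 point of power, or up to about 1.5 if arm SDs and losses also differ. The change should be fixed before outcome data are seen, because adding the term afterwards would invite doubt.

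### Some copilots must cover more than one event, but the primary t-test has no copilot or hospital term, so its standard error may be wrong in either direction

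*Combined protocol and SAP*

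**What the plan says.** The Data analysis section gives one rule for the primary outcome and the other event-level continuous outcomes: "Between-group comparisons for continuous variables will employ two-sided t-tests with unequal variance". It names no term for copilot or hospital.

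On the size of the copilot pool, Research subjects says: "The total number of expected participants is up to 30". Recruitment of copilots is by invitation. Methods/Procedures assigns each event to an arm at random, in blocks by hospital. The control is a silent recorded video. No section says how a copilot is chosen for an event, how many events one physician may cover, or how few physicians would be acceptable.

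The Data elements list for copilots includes the physician's name and "Date/time of each study simulation participation", so repeat participation is foreseen and will be traceable.

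Clustering is recognised at one level only: "Given clustering within simulations, between-group comparisons of survey responses will employ multilevel logistic". Those survey models, logistic or linear, carry a random effect for the event and nothing else.

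The Sample size/power analysis reads "Assuming a baseline no-flow percentage of 0.285" and concludes "we will require 76 mock codes (38 in each arm) to achieve 80% power". The target difference is an absolute fall of 0.09, which the plan equates with 31% in relative terms. It gives no SD, no alpha and no allowance for clustering by copilot.

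**The concern.** The intervention is a person giving advice. Two events covered by the same intensivist share that physician's skill and style, so their no-flow fractions may be correlated. Control events share no such person. The design is therefore partially nested: clustered in one arm, unclustered in the other. The Welch test lets the two arms have different variances, but it still takes the events within each arm to be independent.

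The research question is whether intensivist copilots improve resuscitation, which reaches beyond the particular physicians who took part. If a few of them cover most events, the comparison rests on fewer independent units than 38. A positive within-copilot correlation would then make the interval too narrow and the planned power optimistic. Nothing in the plan prevents that concentration.

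**Working it through.** **Inputs from the documents.** 38 events per arm; 0.09 absolute difference; 80% power; two-sided test; at most 30 copilots; 15% of events lost.

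**Assumptions, because the documents are silent.** Alpha 0.05; intra-copilot correlation (ICC) 0.05 to 0.20; the number of copilots actually used, and how events are shared among them.

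**The plan's own figure.** The 76 cannot be derived forward without an SD, so I solved for it. With the normal approximation, SD = 0.09 × √(38/2) / (1.960 + 0.842) = 0.140 (0.138 with the exact t). The plan is ambiguous on whether 38 is before or after losses. One statement of the sample size says "we will require 76 completed mock codes (38 in each arm) to achieve 80% power"; the other drops the word completed; both cite the 15% loss. If 38 already includes the loss (32/0.85 = 37.6, rounded up to 38), 32 per arm are analysed and the implied SD is 0.128.

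**Forced repeats.** 38 − 30 = 8, so if all 38 events are run, at least eight go to a physician who has already served. The mean is 38/30 = 1.27 events each, or 32/30 = 1.07 if 32 are analysed.

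**Formulas.** Effective cluster size m = Σmᵢ²/Σmᵢ. Copilot-arm design effect DE = 1 + (m − 1) × ICC. Control-arm design effect is 1. The true SE of the difference relative to the Welch SE is r = √((1 + DE)/2). Type I error of the Welch test = 2 × [1 − Φ(1.960/r)]. Power of a test using the correct SE = Φ(2.802/r − 1.960).

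**Effective cluster sizes, 38 copilot events.**
- 30 copilots, even: 22 with one event and 8 with two; (22 + 32)/38 = 1.42.
- 10 copilots, even: 8 with four and 2 with three; (128 + 18)/38 = 3.84.
- 30 on the roster, uptake proportional to 1/rank (about 16 actually used): expected m = 1 + 37 × 0.101 = 4.74, where 0.101 is the sum of squared uptake shares.

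**Results with no hospital effect.**

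| Copilot use | ICC | DE | r | Type I error | Power |
|---|---|---|---|---|---|
| 30, even | 0.05 | 1.02 | 1.005 | 5.1% | 79.6% |
| 30, even | 0.20 | 1.08 | 1.021 | 5.5% | 78.4% |
| 15, even | 0.05 | 1.08 | 1.020 | 5.5% | 78.4% |
| 15, even | 0.20 | 1.33 | 1.078 | 6.9% | 73.8% |
| 10, even | 0.05 | 1.14 | 1.035 | 5.8% | 77.2% |
| 10, even | 0.20 | 1.57 | 1.133 | 8.4% | 69.6% |
| 30, uptake 1/rank | 0.05 | 1.19 | 1.046 | 6.1% | 76.4% |
| 30, uptake 1/rank | 0.20 | 1.75 | 1.172 | 9.4% | 66.7% |

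With 32 events analysed and 30 copilots used evenly, power is 79.5-79.9%. The power column is for a valid 5% test. Welch itself would reject more often (77.1% instead of 69.6% with 10 copilots at ICC 0.20), but only because its error rate is inflated.

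**Hospital blocking.** Balancing arms within hospitals removes between-hospital variation from the difference in means, while the Welch SE still contains it. I simulated 8 hospitals (the plan speaks of 7 to 8) with an assumed hospital ICC of 0.10, 6,000 runs, Monte Carlo error about 0.3 points. At copilot ICC 0.10, Welch type I error was about 4.6% with 30 copilots, 4.6% with 20, 5.0% with 15 and 5.5% with 10, all used evenly. It was about 6 to 6.5% with 1/rank uptake, and about 7% with 10 copilots at copilot ICC 0.20.

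**The case against.** A reader might infer that each intensivist covers several events, so the Welch standard error is too small and the stated 80% power is overstated. The documents do not support that. The one figure they give, up to 30 copilots, allows a mean of 1.27 events each, and recording every participation shows that repeats are possible, not that they are common. At that figure the loss of power is under two points. The larger losses need few copilots or lopsided uptake, together with an ICC that the reviewer supplies.

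Three further points have force. First, ignoring the hospital blocks works in the opposite direction, and the Background itself cites marked variation between hospitals; under even use the Welch test can be conservative. Second, if the copilot does nothing at any event, there is no copilot variance and no inflation. The inflated error rate applies when copilots differ but average to zero, and the consultation is described as standardised, which is meant to limit such differences. Third, with barely more than one event per copilot, the variance component is poorly identified and will often be estimated at zero.

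All of this limits the size and certainty of the concern. It does not remove it. Thirty is a ceiling, participation is voluntary, the trial may run for up to 48 months, and nothing secures even use. An offsetting error of unknown size from the hospital blocks is no safeguard. It is a reason to model both features.

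**Conclusion.** The concern holds in a limited form. The design is partially nested, some repeats are unavoidable if all 38 copilot events are run, and the primary test ignores both copilot and hospital. The consequence ranges from negligible (30 copilots used evenly) to material (about 10 copilots or concentrated uptake: type I error about 6-9%, power about 67-77%, before any hospital effect). These figures rest on assumed ICCs of 0.05-0.20, an assumed two-sided alpha of 0.05, a back-solved SD and assumed patterns of copilot use. Once hospital variation is allowed for, the net direction of the error cannot be settled from the documents. The 80% power is not shown to be wrong. It assumes no copilot clustering and does not say so, and the missing SD and alpha limit any check of it more than the clustering does.

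**What to change.** For the primary and other event-level continuous outcomes, prespecify a linear mixed model with arm, hospital (the blocking factor), a random copilot intercept in the intervention arm only, and arm-specific residual variances. Fit it by REML with Satterthwaite or Kenward-Roger degrees of freedom. Keep the Welch test as a sensitivity analysis. Add the copilot level to the survey models. Spread events over as many consenting copilots as possible, and report the number of copilots and the events per copilot. State in the power paragraph that the 80% assumes no copilot clustering.

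**Cost.** This is mainly SAP wording, since copilot identity, each participation and the event location are already collected; spreading events also needs some scheduling effort. If copilots truly do not differ, simulation of the copilot term (without hospital) put the loss at about 1 point of power with 30 evenly used copilots and about 4 with 10. In 700 runs with copilot variation present, that model held type I error at 4-5% with 10 to 30 copilots. With 8 hospitals, the hospital term uses 8 − 1 = 7 of the 76 − 2 = 74 degrees of freedom; I did not quantify its effect on power.
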